2.1 General Design

This is a single center, double blind randomized cross over design trial that will compare the impact of NAC vs. saline infusion during experimental hypoglycemia on day one on the responses to experimental hypoglycemia on day two. Figure 1 shows the protocol in schematic form. We intend to enroll 18 individuals to obtain the complete data sets from 15 participants.

Expected duration of subject participation is 10-12 weeks. This study will consist of a screening visit and two 2-day intervention visits separated by approximately 8 weeks.

2.2 Primary Study Endpoints

Primary endpoint will be the within person difference in epinephrine secretion during the morning episodes of hypoglycemia on days one and two under the two treatment conditions. Epinephrine secretion during hypoglycemia is assessed by collecting blood samples for measurement of epinephrine concentrations at baseline and every 15 minutes during the period of hypoglycemia (starting at point where blood glucose is first ≤ 55 mg/dl) in the clamp studies done in the mornings of days 1 and 2 of both parts 1 and 2.

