12 PUBLICATION PLAN19

13 REFERENCES20

14 ATTACHMENTS20

List of Abbreviations

List all abbreviations used in protocol

AE	Adverse Event
CFR	Code of Federal Regulations
CRF	Case Report Form
DSMB	Data and Safety Monitoring Board
DSMP	Data and Safety Monitoring Plan
FDA	Food and Drug Administration
GCP	Good Clinical Practice
HIPAA	Health Insurance Portability and Accountability Act of 1996
ICH	International Conference on Harmonisation
IDS	Investigational Drug Services
IRB	Institutional Review Board
PHI	Protected Health Information
SAE	Serious Adverse Event

CONFIDENTIAL

This material is the property of the University of Minnesota. Do not disclose or use except as authorized in writing by the study sponsor

Study Summary

Title	A randomized double blinded study to examine the use of N-acetyl cysteine for the prevention and treatment of HAAF in patients with type 1 diabetes
Short Title	NAC for HAAF
Protocol Number	NA
Phase	I/II
Methodology	This is a single center, double blind randomized cross over design trial that will compare the impact of N-acetyl cysteine (200 mg/kg) vs. saline infusion during experimental hypoglycemia on day one on the responses to experimental hypoglycemia on day two. 18 participants will be studied twice, 8 weeks apart. On each occasion they will undergo a 2 hour hypoglycemic clamp (target 50 mg/dl) in the morning and in the afternoon on day one and then again on the morning of day 2. During the morning clamps, samples will be collected for later measurement of serum epinephrine levels, plasma and red blood cell NAC, cysteine, and glutathione concentrations and GSH/GSSG ratios (redox status), and participants will be asked to complete a hypoglycemia symptom questionnaire
Study Duration	10-12 weeks per subject
Study Center(s)	Single Center
Objectives	Primary endpoint will be the within person difference in epinephrine secretion during the morning episodes of hypoglycemia on days one and two under the two treatment conditions. Epinephrine secretion during hypoglycemia is assessed by collecting blood samples for measurement of epinephrine concentrations at baseline and every 15 minutes during the period of hypoglycemia (starting at point where blood glucose is first \leq 55 mg/dl) in the clamp studies done in the mornings of days 1, 2, and 3 of both parts 1 and 2.
Number of Subjects	36

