Diagnosis and Main Inclusion Criteria	Healthy adults ages 18-65 years with hemoglobin A1c < 6.0%. Exclusion criteria will include history of diabetes, hyperglycemia, stroke, seizures, arrhythmias, active cardiac disease; pregnancy or plan to become pregnant during the study period; diagnosis of asthma; use of anti-oxidants or drugs that can alter glucose metabolism; and concomitant medical problems that may prevent the subject from successfully completing the protocol.
Study Product, Dose, Route, Regimen	N-acetyl cysteine 200 mg/kg (or saline) IV infusion (given as a 150 mg/kg loading dose over the first hour and then followed by a 50 mg/kg maintenance dose infused over the next 4 hours on day 1 of each of the two parts of the study)
Duration of administration	5 hours on day one

Reference therapy	NAC will be tested against placebo.
Statistical Methodology	
Our primary outcome is the peak epinephrine response during the third hypoglycemic clamp of each infusion experiment, thus each participant will have two observations: one from their NAC infusion experiment and one from their saline infusion experiment. We will fit a general linear mixed model with fixed effects for treatment (NAC vs. saline), treatment order (NAC first vs. saline first), and period (Part 1 vs. Part 2) and a random effect for participant. We will also consider adjustment for important baseline characteristics, such as age, gender, and duration of diabetes. Diagnostics will be examined to assess model assumptions. Secondary outcomes include: the within-person difference in peak epinephrine response between the first hypoglycemic clamp (when an infusion is given) and the third hypoglycemic clamp (when no infusion is given) of each infusion experiment; symptom scores during the third hypoglycemic clamp of each infusion experiment; and the within-person difference in symptom scores between the first hypoglycemic clamp and the third hypoglycemic clamp of each infusion experiment

CONFIDENTIAL

1 Introduction

This document is a protocol for a human research study. This study will be conducted according to US and international standards of Good Clinical Practice (FDA Title 21 part 312 or 812 and International Conference on Harmonisation guidelines), applicable government regulations and Institutional research policies and procedures.

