6.1 Sample Size Determination

We propose a two-period two-treatment cross-over study, where each participant gets NAC infusion and saline infusion, in randomized order as shown in Figure under 2.1. Our primary outcome is the peak epinephrine response during the third hypoglycemic clamp of each infusion experiment, thus each participant will have two observations: one epinephrine response from their NAC infusion experiment and one epinephrine response from their saline infusion experiment. We expect to recruit 18 individuals in order to complete 15 studies. Additional participants will be recruited if needed to have 15 completed studies. If NAC prevents HAAF, then the epinephrine response during the third hypoglycemic clamp after NAC infusion will still be high, while the epinephrine response during the third hypoglycemic clamp after saline infusion will be blunted. Therefore ***this within-person difference in epinephrine response will be large and positive***. Assuming a one-sided type I error of 5% and a power of 85%, we can detect an epinephrine response difference between NAC and saline of at least 154 units. This magnitude of difference is comparable to the difference between healthy controls and subjects with T1DM and hypoglycemia unawareness that we found in a previous study. In that study, participants underwent a hyperinsulinemic hypoglycemic clamp and the epinephrine response during hypoglycemia in the subjects with T1DM was 121 ± 168 pg/ml vs. 278 ± 134 pg/ml in controls.

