6.2 Statistical Methods

Our primary outcome is the peak epinephrine response during the third hypoglycemic clamp of each infusion experiment, thus each participant will have two observations: one from their NAC infusion experiment and one from their saline infusion experiment. We will fit a general linear mixed model with fixed effects for treatment (NAC vs. saline), treatment order (NAC first vs. saline first), and period (Part 1 vs. Part 2) and a random effect for participant. We are confident that our study design, with a washout period of 8 weeks between Parts 1 and 2, has minimized the possibility of a treatment effect from Part 1 that lingers into Part 2. We will also consider adjustment for important baseline characteristics, such as age, gender, and duration of diabetes. Diagnostics will be examined to assess model assumptions. Secondary outcomes include: the within-person difference in peak epinephrine response between the first hypoglycemic clamp (when an infusion is given) and the third hypoglycemic clamp (when no infusion is given) of each infusion experiment; symptom scores during the third hypoglycemic clamp of each infusion experiment; and the within-person difference in symptom scores between the first hypoglycemic clamp and the third hypoglycemic clamp of each infusion experiment.

CONFIDENTIAL

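### The primary endpoint is stated inconsistently: section 2.2 uses epinephrine on the mornings of days 1 and 2, while 6.1 and 6.2 use the third-clamp peak and attach alpha, power and the model to that alone

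*Combined protocol and SAP*

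**What the plan says.** Three places give one form of the primary endpoint. Section 2.2 reads: "Primary endpoint will be the within person difference in epinephrine secretion during the morning episodes of hypoglycemia on days one and two". The comparison is between NAC and saline. The Primary Objective (after 1.5) and the Objectives row of the Study Summary open with the same sentence. None says whether secretion means a peak, a mean or an area under the curve. The sentence that follows sets the sampling: a baseline sample, then one every 15 minutes, "starting at point where blood glucose is first ≤ 55 mg/dl".

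Three other places give a second form. The Statistical Methodology row of the Study Summary, 6.1 and 6.2 all say: "Our primary outcome is the peak epinephrine response during the third hypoglycemic clamp of each infusion experiment". Each participant then contributes two observations, one per treatment. Section 5 puts two clamps on day 1 and one on day 2, so the third clamp is the day 2 morning clamp.

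Section 6.2 and the Statistical Methodology row then rank another quantity lower. The entry begins: "Secondary outcomes include: the within-person difference in peak epinephrine response between the first hypoglycemic clamp (when an infusion is given". The other end of that difference is the third clamp.

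The error rate and power are in 6.1: "Assuming a one-sided type I error of 5% and a power of 85%, we can detect an epinephrine response difference between NAC and saline". The size given there is 154 units or more, with 15 completers.

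**The concern.** The natural reading of 2.2 is the change from the day 1 morning to the day 2 morning, compared between NAC and saline. That is the quantity 6.2 lists as secondary, and no passage reconciles the two rankings. At reporting, either result could be cited as the prespecified primary one.

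The two quantities can give different answers. The third-clamp comparison uses day 2 values only, with no infusion running. The change subtracts a day 1 value taken while NAC or saline is being infused, so an acute effect of NAC on that day would enter the primary contrast. Section 5 also describes different clamps on the two mornings, a single 50 mg/dl target on day 1 and stepped targets on day 2, so the change would also reflect a different stimulus.

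A smaller gap lies inside the second form. Response could mean the peak value or the rise from baseline. A baseline sample is drawn, but the choice is not stated.

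**Working it through.** **1. Which quantity has a test behind it.**

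| Item | Third-clamp peak | Day 1 to day 2 change |
|---|---|---|
| Called primary in | Statistical Methodology row, 6.1, 6.2 | 2.2, Primary Objective, Objectives row (natural reading) |
| Called secondary in | nowhere | Statistical Methodology row, 6.2 |
| Summary measure | peak | none where primary; peak where secondary |
| Alpha, power, difference | 6.1 | none |
| Model | 6.2, two observations per person | none stated |

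The 154 units belong to the left column. Section 6.1 explains them by expecting that "the epinephrine response during the third hypoglycemic clamp after NAC infusion will still be high" while the response after saline is blunted. The 6.2 model has terms for treatment, order, period and participant. It has no day or clamp term, so no day 1 value enters it.

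**2. Reproducing 6.1.** Inputs from 6.1: SDs 168 and 134 pg/ml from a previous study, 15 completers, one-sided 5%, 85% power. The SD of the within-person difference is not given. Assume a common SD s per clamp and zero correlation between parts.

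- s = √((168² + 134²)/2) = 152.0
- SD of the NAC minus saline difference = s√2 = 214.9
- Noncentrality at 154 = 154 × √15 / 214.9 = 2.775
- Noncentral t with 13 df, critical value 1.771: power 0.837 (0.840 with 14 df)
- Detectable difference at 85% power = 2.833 × 214.9 / √15 = 157.2

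So 154 units at 85% power is roughly reproduced.

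**3. The same sum for the change.** The contrast is (day 2 − day 1 on NAC) − (day 2 − day 1 on saline). With equal SDs s on all four mornings, its variance is 4s²(1 − rw − rb + rx). Here rw is the correlation between mornings within a part, rb between parts on the same day, and rx between parts across days. The documents give none of these. Setting rb = rx leaves 4s²(1 − rw):

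| Assumed rw | SD of contrast | Power at 154 | Detectable at 85% |
|---|---|---|---|
| 0 | 303.9 | 0.585 | 222.3 |
| 0.3 | 254.3 | 0.718 | 186.0 |
| 0.5 | 214.9 | 0.837 | 157.2 |
| 0.7 | 166.5 | 0.959 | 121.8 |

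Other valid assumptions favor the change. With rw = 0.6, rb = 0.5 and rx = 0.3 its SD is 135.9. The third-clamp difference at the same rb = 0.5 has SD √(2s² × 0.5) = 152.0. Power at 154 is then 0.994 against 0.981.

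**4. Acute effect on day 1.** Let NAC shift the day 1 morning response by a relative to saline, and the day 2 response by d. The third-clamp contrast estimates d. The change contrast estimates d − a. A negative a could make the change look favorable with no day 2 benefit, and a positive a could hide a real one. The documents give neither the sign nor the size of a.

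**The case against.** The strongest reply is that the intended analysis can be identified. The Statistical Methodology row, 6.1 and 6.2 agree on outcome and contrast. Section 2.1 states the aim as the effect of the day 1 infusion on the day 2 response. A statistician who follows section 6 has an outcome, a model and an expected direction. This stands, and it narrows the risk to the use of 2.2 when results are reported. It does not remove the problem, because the objective and endpoint sections still rank the outcomes differently from 6.2.

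A reader might infer more than the documents support:

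- *That the two definitions are incompatible.* They share the day 2 morning clamp. They are inconsistent and unreconciled, but they overlap.
- *That 2.2 sets up two primary tests, one per morning, with an inflated error rate.* No passage proposes a separate test on each morning, and 2.2 speaks of one endpoint and one difference. No multiplicity charge should rest on it.
- *That the trial is underpowered for the 2.2 endpoint.* The table spans 0.58 to 0.96 on assumed correlations, and another set gives 0.99. Equal SDs on both mornings is also doubtful, given the different clamps in section 5.
- *That 6.1 is wrong.* It is roughly reproduced.

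**Conclusion.** The point holds. On the natural reading of 2.2, the same quantity is primary there and secondary in 6.2, and nothing in the documents settles which ranking governs. This rests on the text alone and needs no assumption about variances.

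The calculations support one further statement only: power for the day 1 to day 2 change is not established. The range of about 0.58 to 0.96 at 154 units depends on assumed within-part correlations of 0 to 0.7, equal cross-part correlations, equal SDs on both mornings and 15 completers. It is not evidence of a shortfall. Separately, the change mixes the day 2 effect with any acute NAC effect on day 1 and with the difference in clamp targets. The third-clamp peak does not carry the day 1 effect, and it matches the aim in 2.1. It is therefore the better supported choice of primary endpoint. This must be fixed before unblinding.

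**What to change.** Before unblinding, by a dated amendment that gives the reason:

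- In the Study Summary Objectives row, the Primary Objective and 2.2, replace the first sentence with: *Primary endpoint: peak epinephrine response during the third (day 2 morning) hypoglycemic clamp, NAC versus saline within person, analyzed as in 6.2.*
- Keep the sampling sentence that follows. Those three places are the only ones that state the ≤ 55 mg/dl window.
- State once whether response is the peak value or the rise from baseline, and use that meaning in 6.1 and 6.2.
- Keep the first-to-third-clamp difference as secondary, with a note that it includes any acute infusion effect on day 1 and the difference in clamp targets.

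The cost is a wording amendment that goes to the IRB (section 10). No participants, samples or procedures are added.

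Separate editorial points should be reconciled at the same time, but they do not bear on the conclusion. The Objectives row places sampling "in the clamp studies done in the mornings of days 1, 2, and 3 of both parts 1 and 2", and section 5 opens with 3-day visits, while 2.1 and the visit table describe 2-day visits. Section 2.3 does not list "symptom scores during the third hypoglycemic clamp of each infusion experiment" as its own outcome, although 6.2 does. Section 5 collects a score at each day 2 step without saying which is analyzed. The Study Summary gives a 50 mg/dl target for the day 2 clamp, while section 5 gives stepped targets.

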2.3 Secondary Study Endpoints

Secondary endpoint will be within person difference in symptom scores collected during the morning episodes of hypoglycemia on days one and two under the two treatment conditions. Symptom scores during hypoglycemia will be quantified using a previously validated questionnaire at baseline and at the end of the hypoglycemic clamp studies done in the mornings of days 1 and 2 of both parts 1 and 2.

2.4 Primary Safety Endpoints

The safety endpoint is ascertainment of symptoms related to allergic reactions (pruritus, swelling/tingling of mouth or tongue, shortness of breath) at baseline and at 30, 60, and 90 minutes after the start of the NAC/saline infusion. Participants' symptoms will be ascertained by the use of a standardized questionnaire.

3 Subject Selection and Withdrawal

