1.5 Dose Rationale and Risk/Benefits

This is a proof of principle experiment in which the maximal dose of NAC approved for human use will be intravenously infused to ensure that high serum concentrations of the drug are achieved. We propose a 200 mg/kg dose in which we will infuse a 150 mg/kg loading dose over the first hour followed by a 50 mg/kg maintenance dose infused over the next 4 hours, as is recommended for acetaminophen overdose,

In the package insert, the manufacturer includes a table that lists the incidence of drug related adverse events following drug administration. Data from 180 individuals are included in the table; 10 experienced mild anaphylactoid reactions (6%), 16 experienced moderate reactions (9%) and 2 experienced severe reactions (1%). All of these reactions occurred within the first 2 hours following the drug administration, following a dosage schedule we plan to use for this protocol. The package insert also includes a table that summarizes the adverse events observed in 76 published articles in which NAC was intravenously infused. The Rocky Mountain Poison and Drug Center prepared this table from information collected on 2040 subjects. 1.67% were noted to have urticaria, 1.47% had vasodilatation and rash, 0.78% had hypotension. Our protocol excludes individuals with asthma or with a history of bronchospasm in an effort to reduce the risk of severe anaphylactoid reactions. We believe the small risk of adverse events from NAC exposure are reasonable given the impact of hypoglycemia unawareness on patients with diabetes. The first sign that these patients have hypoglycemia is confusion or loss of consciousness, both of which can lead to injury from accidents. If untreated, this hypoglycemia could cause seizures and death. The number of patients with type 1 diabetes who experience hypoglycemia unawareness has been estimated to be as high as 25%.

Primary Objective

Primary endpoint will be the within person difference in epinephrine secretion during the morning episodes of hypoglycemia on days one and two under the two treatment conditions. Epinephrine secretion during hypoglycemia is assessed by collecting blood samples for measurement of epinephrine concentrations at baseline and every 15 minutes during the period of hypoglycemia (starting at point where blood glucose is first ≤ 55 mg/dl) in the clamp studies done in the mornings of days 1 and 2 of both parts 1 and 2.

Secondary Objective

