4.2 Treatment Regimen

A 150 mg/kg loading dose of NAC or saline over the first hour followed by a 50 mg/kg maintenance dose infused over the next 4 hours on days one of both parts of the study.

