7.2 Recording of Adverse Events

At each contact with the subject, the investigator must seek information on adverse events by specific questioning and, as appropriate, by examination. Information on all adverse events will be recorded immediately in the source document, and also in the appropriate adverse event module of the case report form (CRF). All clearly related signs, symptoms, and abnormal diagnostic procedures results will be recorded in the source document, though should be grouped under one diagnosis.

All adverse events occurring during the study period must be recorded. The clinical course of each event will be followed until resolution, stabilization, or until it has been determined that the study treatment or participation is not the cause. Serious adverse events that are still ongoing at the end of the study period must be followed up to determine the final outcome. Any serious adverse event that occurs after the study period and is considered to be possibly related to the study treatment or study participation should be recorded and reported immediately.

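### The structured allergy endpoint in Section 2.4 is shorter and narrower than the reaction profile in Section 1.5, leaving the remainder to unscheduled adverse event reporting

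*Combined protocol and SAP*

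**What the plan says.** Section 2.4 makes the primary safety endpoint the ascertainment of "symptoms related to allergic reactions (pruritus, swelling/tingling of mouth or tongue, shortness of breath"), by standardized questionnaire, "at baseline and at 30, 60, and 90 minutes after the start of the NAC/saline infusion".

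Section 1.5 gives two sets of safety data from the package insert:

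- A table of 180 individuals, with 10 mild, 16 moderate and 2 severe anaphylactoid reactions. Of these it says: "All of these reactions occurred within the first 2 hours following the drug administration", on the dosage schedule planned here.
- A separate table of 2040 subjects from published articles, in which "1.67% were noted to have urticaria, 1.47% had vasodilatation and rash, 0.78% had hypotension". No timing or dose schedule is given for this table.

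The Study Summary gives the duration of administration as "5 hours on day one". Section 5 schedules glucose, hormone and redox sampling and hypoglycemia symptom scores. It does not mention the allergy questionnaire, a skin check or a blood pressure reading.

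General adverse event collection is separate. Section 7.1 counts any new or worsening symptom or sign as an adverse event, with reporting to 30 days after the last study treatment. Section 7.2 adds: "At each contact with the subject, the investigator must seek information on adverse events by specific questioning and, as appropriate, by examination". Under Section 7.5 an unblinded DSMB reviews early infusion stops and all adverse events at least monthly.

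**The concern.** Section 1.5 tells the reader which reactions to expect and when. Section 2.4 then sets up an instrument whose last administration comes before the end of that time window and whose items leave out some of those reactions. Vasodilatation, rash and hypotension are quantified in 1.5 but are not among the three symptom groups. A fall in blood pressure without symptoms would be found only if someone measured it, and no measurement is scheduled.

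What is at stake is the quality of the comparison. A blinded crossover can set NAC against saline in the same person, which is useful with 18 participants, but only if the same items are collected at the same times in both periods. After 90 minutes, and for skin and blood pressure findings at any time, the plan relies on reporting with no fixed times. If reactions attributable to NAC fall in that part, the endpoint counts fewer of them on NAC while the saline count is little affected, and the difference shrinks.

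**Working it through.** **Inputs**

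- Questionnaire times: 0, 30, 60 and 90 minutes from infusion start (2.4).
- Reaction window: 2 hours = 120 minutes (1.5, 180-person table). Counting it from infusion start is an assumption, because 1.5 does not define the starting point.
- Infusion length: 1 hour + 4 hours = 300 minutes (4.2).
- Rates: urticaria 1.67%, vasodilatation and rash 1.47%, hypotension 0.78% (1.5, 2040-subject table).
- NAC exposures: 18, one per participant (2.1 and 6.1), or 15 if only completers are counted. One row of the Study Summary gives 36 subjects; I use 18, as do 2.1, 6.1 and the stopping table in 7.5.

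**1. The plan's own figures.** 10/180 = 5.6%, 16/180 = 8.9% and 2/180 = 1.1%, which round to the stated 6%, 9% and 1%. Together, 28/180 = 15.6%.

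**2. Timing.** The part of the window after the last questionnaire is (120 − 90)/120 = 30/120 = 25%. Section 1.5 gives no breakdown within the 2 hours, so the number of the 28 cited reactions that came after 90 minutes could be anything from 0 to 28.

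**3. Content.** Setting the 1.5 list against the 2.4 items:

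| Reaction in 1.5 | Covered by a 2.4 item? |
|---|---|
| Urticaria | Possibly in part, through the pruritus item |
| Vasodilatation and rash | Not named; rash possibly in part, through pruritus |
| Hypotension | No |

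**4. Chance that an event of the omitted types occurs.** P(at least one) = 1 − (1 − p)^n, assuming the 1.5 rates apply here and participants are independent.

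| Event | p | Expected, n = 18 | P, n = 18 | P, n = 15 |
|---|---|---|---|---|
| Hypotension | 0.0078 | 0.14 | 1 − 0.9922^18 = 13% | 11% |
| Vasodilatation and rash | 0.0147 | 0.26 | 1 − 0.9853^18 = 23% | 20% |
| Either, if no overlap | 0.0225 | 0.41 | 1 − 0.9775^18 = 34% | 29% |

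These are probabilities that an event occurs, not that it goes unrecorded.

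**5. Feasibility of a later check.** Section 5 starts the morning clamp 30 minutes into the infusion. At 2 hours long, it runs from minute 30 to minute 150. At minute 120 the participant is therefore in the clamp, with glucose drawn every 5 minutes. The afternoon clamp starts 2 hours after the morning one ends, at minute 270, so the participant is also on site when the infusion ends at minute 300.

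**The case against.** The strongest reply is that nothing is lost. Rash, hypotension and any reaction after 90 minutes meet the adverse event definition in 7.1. They must be sought by questioning and, where appropriate, examination under 7.2, and the DSMB reviews them under 7.5. The stopping rule in 7.5 covers any allergic symptoms severe enough to stop the infusion; its named symptoms are examples, and it has no 90-minute limit. Investigators witness treatment (4.4). On this view, what goes on a form and what is left to adverse event reporting is a design preference in a small proof-of-principle study.

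Most of this stands, and it rules out several stronger readings that a reader might infer:

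- *That the plan does not collect these reactions.* It does, as adverse events. They lie outside the structured endpoint only.
- *That 25% of the window, or (300 − 90)/300 = 70% of the infusion, is unobserved.* Staff are at the bedside through minute 150 at least. What is absent is a scheduled questionnaire. Section 1.5 also gives no support for a risk window beyond 2 hours, so the 70% does not measure missed risk.
- *That late reactions are known to be missed.* An upper limit of 2 hours does not show that any reaction came after 90 minutes.
- *That rash and hypotension share the 2-hour window.* The window belongs to the 180-person table and those rates to the other.
- *That the omitted risk is larger once urticaria is added* (1.67% + 1.47% = 3.14%, or 44% in 18 exposures). Urticaria may be partly caught by the pruritus item, and this too is a chance of occurrence.

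The rates may also not carry over. Section 5 gives diphenhydramine just before the infusion and Section 3.2 excludes asthma, while 1.5 does not say whether the cited patients were comparable in these respects.

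What the reply does not answer is matched ascertainment. Section 7.2 sets no times within the infusion and names no measurement, so it does not ensure that the NAC and saline periods are examined alike.

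**Conclusion.** The point holds as a mismatch between Sections 2.4 and 1.5 that is cheap to correct. It is not a failure to collect safety data. The scheduled endpoint stops 30 minutes short of the 120-minute window in 1.5, if that window is counted from infusion start, and it omits skin findings and blood pressure. Any NAC-saline comparison of the endpoint can therefore understate the difference. By how much is not known: the share lost through timing is anywhere from none to all of the cited reactions. The occurrence figures (13% for hypotension, 23% for vasodilatation and rash, 34% for either without overlap) rest on the 1.5 rates applying to 18 premedicated healthy volunteers, each given NAC once.

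**What to change.** - In Section 2.4, add the same questionnaire at 120 minutes.
- At each questionnaire time, record observed skin findings (urticaria, flushing, rash) and a cuff blood pressure, identically in both periods.
- List the questionnaire and these assessments in Section 5, where none now appears.
- Reconcile 2.4, 1.5, 5 and 7, stating which reactions belong to the structured endpoint and which are left to general adverse event reporting.
- An end-of-infusion questionnaire is optional, because 1.5 does not support a window beyond 2 hours.

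These are measurements for an endpoint; no dose, treatment or stopping rule changes. The cost is a short protocol edit, a few lines on an existing form, and a few minutes of staff time per infusion while the participant is already in the clamp.
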